10.5 DSMB Statistical Monitoring Rules

Safety monitoring of the accumulated outcomes data is designed to ensure the continuing safety of the currently enrolled participants and participants not yet enrolled. This is achieved by stopping the trial early to reduce the number of participants exposed to a harmful or ineffective treatment.

10.5.1 Non-efficacious Treatment (Futility)

Due to small sample size and somewhat longer evaluation time it is not practical to stop the trial for futility. Therefore we do not use a group sequential approach for monitoring efficacy (Cytel, 2002).

10.5.2 Toxic Treatment (Safety)

We plan to monitor toxicity within each arm. The cumulative number of grade 3 or 4 toxic events will be monitored after each person is enrolled (Ray and Rai, 2011 & 2012). If the cumulative number of toxic events produces enough evidence to conclude that the

true toxicity rate is greater than or equal to 33% ($Pt0 = 0.33$) then the trial will be stopped early for safety reasons. The cumulative number of toxic events after each patient is treated will be compared to the boundary values in Table S2. If the cumulative number of toxic events after person i is treated is greater than or equal to the associated boundary value bi then the combination treatment is rejected for safety considerations. With this rule, there is only a 5% chance of stopping the trial early for lack of safety if the true toxicity rate is less than 33%. Continual assessment of the toxic events ensures we do not expose an undue number of patients to a harmful treatment. This is a conservative approach. Another approach will be using the method of Ray and Rai (2013) when monitoring will be done at the time of DSMB reports, which will be flexible and used at that stage the proportion of subjects experiencing SAEs.

Table S2. Toxicity Boundaries, N = 44, Pt0 = 0.33, and alpha=0.05

Minimum Number of Subjects	Maximum Number of Subjects	Number of Toxicities
4	4	4
5	6	5
7	7	6
8	9	7
10	11	8
12	14	9
15	16	10
17	18	11
19	19	12
20	22	13
23	23	14
24	27	15
28	28	16
29	30	17
31	32	18
33	34	19
35	37	20
36	40	21
41	42	22
43	44	23

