2.2 Supporting Data in Humans

Recent retrospective human aSAH studies evaluating the Maryland low-dose IV heparin (LDIVH) protocol provide evidence that heparin may reduce the incidence of symptomatic vasospasm requiring rescue therapy, vasospasm related CT infarction, and cognitive dysfunction. In [name] et al. (J Neurosurg 119:1611-1619) an analysis of 86 Fisher grade 3 aSAH patients treated with craniotomy and clipping was performed. The patients were enrolled concurrently and 43 LDIVH patients were compared to 43 control patients. The incidence of clinical vasospasm in the control group was 47%, and 9% in the LDIVH group ($p=0.0002$). When evaluating for CT evidence of vasospasm related infarction, there was a 21% incidence of CT infarct in the control group, and 0% incidence of CT infarct in the LDIVH treated group ($p=0.003$).

There were no hemorrhagic complications. Unpublished study data ([name]) presented during a symposium at the 2015 AHA/ASA International Stroke Conference demonstrated a significantly better ($p=0.013$) mean MoCA score of 26.4 in the LDIVH treated group ($n=25$) compared to 22.7 in the control group ($n=22$). [MoCA score range 0-30, normal 26-30]. A 3-point difference in mean MoCA scores is considered clinically relevant. The influence of heparin on MoCA remained significant after controlling for potential confounding factors with multivariate regression analysis. Additional preliminary data demonstrate that the Maryland LDIVH protocol can also mute elevations of the inflammatory biomarker myeloperoxidase (MPO) at 48 hours ([name], unpublished data). MPO has been previously identified to be elevated in serum after aSAH and at even higher levels in those patients with cerebral vasospasm. The Maryland LDIVH protocol has been administered to over 200 patients without any serious adverse safety concerns.

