8.2 REPORTING OF ADVERSE EVENTS / REACTIONS

Adverse events are generally detected in two ways:

Clinical: Symptoms reported by the subject or signs detected on examination.

Ancillary testing: abnormalities of vital signs, laboratory tests, and other diagnostic procedures (other than outcome measures: the results of which are not being captured as AEs).

Assessment of Clinical Adverse Events

At each visit including the 90 day follow-up visit, the subject will be asked “Have you had any problems or symptoms since your last visit?” in order to determine the occurrence of adverse events. If the subject reports an adverse event, the Investigator will determine:

1. Type of event
2. Date of onset and resolution (duration)
3. Severity (mild, moderate, severe)
4. Seriousness (does the event meet the above definition for an SAE)
5. Causality, relation to investigational product and disease
6. Action taken regarding investigational product
7. Outcome

Relatedness of Adverse Event to Investigational Product

The relationship of the AE to the investigational product should be specified by the Site Investigator or the CEC, using the following definitions:

1. **Definitely Not Related:** Concomitant illness, accident or event with no reasonable association with treatment.
2. **Unlikely (probably not related):** The reaction has little or no temporal sequence from administration of the investigational product, and/or a more likely alternative etiology exists.
3. **Possibly Related:** The reaction follows a reasonably temporal sequence from administration of the investigational product and follows a known response pattern to the suspected investigational product; the reaction could have been produced by the investigational product or could have been produced by the subject’s clinical state or by other modes of therapy administered to the subject. (suspected ADR)
4. **Probably Related:** The reaction follows a reasonably temporal sequence from administration of investigational product; is confirmed by discontinuation of the investigational product or by re-challenge; and cannot be reasonably explained by the known characteristics of the subject’s clinical state. (suspected ADR)

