8.5 DEFINITIONS AND MANAGEMENT OF BLEEDING / HEMORRHAGE EVENTS

We have chosen to follow formal guidelines set forth by the International Society of Thrombosis and Haemostasis for bleeding complications (Schulman S, et al. *J Thromb Haemost* 2005;3(4):692-694). The normal rate of major bleeding or clinically relevant non-major bleeding in aSAH patients with protected aneurysms is estimated at approximately 10-20% (EVD insertion/tract hemorrhages, femoral artery access complications, GI bleed, fall out of bed, nasopharyngeal feeding tube insertion, etc.).

Bleeding complications are defined as:

Any development of clinically relevant non major bleeding or major bleeding, as defined by the International Society of Thrombosis and Haemostasis (ISTH):**a) Major Bleeding (≥ 1 of the following in 24 hr time period):**

- i) Bleeding causing a fall in hemoglobin level of 2 g/dL or more, or leading to transfusion of two or more units of whole blood or red cells.
- ii) Symptomatic bleeding in a critical area or organ, such as intracranial, intraspinal, intraocular, retroperitoneal, intraarticular or pericardial, or intramuscular with compartment syndrome, and/or
- iii) Fatal bleeding

b) Clinically Relevant Non-Major Bleeding

- i) Acute or sub-acute clinically overt bleeding that does not satisfy the criteria for major bleeding and leads to physician-guided medical or surgical treatment for bleeding, or a change in antithrombotic therapy (including study drug) for bleeding.

c) Minor Bleeding

- i) All acute clinically overt bleeding events not meeting the criteria for either major bleeding or clinically relevant non-major bleeding are classified as minor bleeding.

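### The Table S2 stopping rule in section 10.5.2 counts an undefined event, lets a crossing in either arm stop the trial, and uses a 33% threshold that fits the expected bleeding rate poorly

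*Protocol*

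**What the plan says.** Section 10.5.2 sets the arm, event, threshold and consequence of the continuous safety rule:

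- Arm and event: "We plan to monitor toxicity within each arm. The cumulative number of grade 3 or 4 toxic events will be monitored after each person is" entered.
- Threshold: enough evidence that the "true toxicity rate is greater than or equal to 33" per cent.
- Consequence: "then the trial will be stopped early for safety reasons". A later sentence gives a second consequence, rejection of a combination treatment.

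Table S2 gives the boundary for N = 44, Pt0 = 0.33 and alpha = 0.05, running from 4 of 4 patients to 23 of 43-44. The section states a 5% chance of stopping when the true rate is below 33%. It adds an alternative for DSMB reports based on the proportion of subjects with SAEs, again without attribution.

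Elsewhere, section 8.2 lists the severity item as "Severity (mild, moderate, severe"), and sections 8.1 and 8.2 have relatedness to study drug assigned by the site and adjudicated by the events committee (CEC). Section 8.5 says: "The normal rate of major bleeding or clinically relevant non-major bleeding in aSAH patients with protected aneurysms is estimated at approximately 10-20" per cent. Section 8.6 ties a DSMB recommendation to terminate to the LDIVH arm being unsafe.

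**The concern.** A stopping rule has to say which events count, in whom, and against what rate. Here each of these is either undefined or does not match the rest of the protocol.

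Grades 3 and 4 belong to a scale that the protocol does not otherwise use. The protocol defines an adverse drug reaction and collects causality, but the rule uses neither. Controls receive subcutaneous heparin as standard care and no study infusion, yet their events can end the trial, and the two arms are never compared. Bleeding is the primary safety endpoint and a condition of study success, but the rule does not name it.

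If the event is read narrowly, the rule may miss the harm of most interest. If it is read broadly, it may stop the trial for complications of the hemorrhage itself.

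**Working it through.** **Inputs.** Table S2 boundaries b(n), N = 44 per arm, Pt0 = 0.33 (10.5.2). Bleeding background 10-20% (8.5). Clinical vasospasm 47% in controls and 9% on LDIVH in an earlier clipped cohort (2.2). The protocol gives no all-cause severe event rate, so 30-60% is assumed. Each patient counts at most once.

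**Method.** Let f(n,k) be the probability that k of the first n patients have had an event with no earlier crossing. Then f(n,k) = (1 − p)·f(n−1,k) + p·f(n−1,k−1). After each n, any mass with k ≥ b(n) is removed and added to the stopping probability. For example, at p = 0.33 the first look adds 0.33⁴ = 1.2%.

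**The plan's own figure.** At p = 0.33 the total is 5.31%, or 5.29% if the overlapping rows (35-37 and 36-40) are resolved the other way. The stated 5% is reproduced to the nearest whole per cent, and the overlap hardly affects it. The 5% is per arm: with both arms at 33%, the chance that at least one crosses is 1 − (1 − 0.0531)² = 10.3%.

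**Reading A: only bleeding counts.**

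| Background | Control arm crosses | Doubled on LDIVH | LDIVH arm crosses |
|---|---|---|---|
| 10% | 0.01% | 20% | 0.3% |
| 15% | 0.08% | 30% | 2.9% |
| 20% | 0.3% | 40% | 18.5% |

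The control arm almost never crosses, but the rule is also weak against a doubling of bleeding on LDIVH.

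**Reading B: severe events of any cause count.**

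| Event rate in an arm (assumed) | That arm crosses |
|---|---|
| 30% | 2.9% |
| 40% | 18.5% |
| 47% | 45.6% |
| 50% | 59.6% |
| 60% | 93.1% |

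The 47% row borrows the vasospasm rate in "The incidence of clinical vasospasm in the control group was 47%, and 9% in the LDIVH group" and assumes that every such case would be grade 3-4.

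**Can the two results hold together?** Add bleeding to a disease background d, assuming independence: p = 1 − (1 − d)(1 − bleeding rate). With d = 30% in both arms:

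| Bleeding, control to LDIVH | p control | p LDIVH | Control crosses | LDIVH crosses |
|---|---|---|---|---|
| 10 to 20% | 0.37 | 0.44 | 11.2% | 32.5% |
| 15 to 30% | 0.405 | 0.51 | 19.9% | 64.1% |
| 20 to 40% | 0.44 | 0.58 | 32.5% | 89.0% |

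With an equal background, the LDIVH arm crosses more often. The reverse needs a much lower disease rate on LDIVH. With 47% against 9% and bleeding of 10% against 20%, the control arm has p = 1 − 0.53 × 0.90 = 0.523 and crosses with probability 70%. The LDIVH arm has p = 1 − 0.91 × 0.80 = 0.272 and crosses with probability 1.6%.

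**The case against.** - **Toxic may already mean drug-related.** The section heading concerns toxic treatment, and section 8.2 keeps test results that are outcome measures out of adverse event capture. That reading is natural, so it cannot be said that the rule counts events whatever their cause. What stands is that the text does not settle it, and that the alternative in the same section counts SAEs without attribution.
- **Controls also receive heparin.** They get subcutaneous prophylaxis, and section 6.9 places both groups at risk of heparin-induced thrombocytopenia. Watching both arms is therefore sensible. It does not follow that a control-arm crossing should stop the trial.
- **The 47% is a weak guide.** It comes from a retrospective clipped cohort, whereas this trial excludes clipping and enrolls WFNS grades 1-2. This stands, which is why a range is shown.
- **Other safeguards exist.** The DSMB can halt the study for patient safety (8.2), and its charter overrides the protocol (8.6). The CEC forwards dangerous trends (section 8), and the medical safety monitor can go directly to the DSMB chair (12.4). This stands and limits the consequence.
- **Attribution is open to bias in unblinded care.** This also stands. It is a reason to count bleeding without attribution and to require relatedness only for other events.

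**Conclusion.** The concern holds as a fault in the stated rule, not as a missing detail: section 10.5.2 itself fixes the arms, event, threshold, boundary and consequence. The event matches no severity scale in the protocol, the effect of a control-arm crossing conflicts with section 8.6, and one stated consequence refers to a treatment this trial does not have.

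How the rule performs depends on the definition it lacks. If bleeding alone counts, it stops on a doubling with probability 0.3-18.5% across the protocol's own background range. If all severe events count, the chance that an arm crosses goes from 2.9% at an assumed 30% to 93% at 60%. All figures assume one count per patient.

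A reader might infer that control-arm disease events will stop the trial while doubled bleeding on heparin almost never will. The documents do not support that. The first half needs all causes to count and the second needs bleeding alone to count. Under all-cause counting with an equal background, LDIVH crosses more often than control. The two hold together only if LDIVH has a much lower disease-event rate. Almost never also overstates the case for a doubling from 20%, where the probability is 18.5%.

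**What to change.** 1. Make the LDIVH arm the only trigger, show control-arm rates to the DSMB as the comparator, and replace combination treatment with LDIVH. Reconcile this wording with section 8.6.
2. Define the counted event with data the trial already collects. One option is a patient with at least one ISTH major or clinically relevant non-major bleed, or an SAE that the CEC judges at least possibly related. Count it when reported and through discharge, not only at the end of infusion. Use site causality provisionally until adjudication.
3. Have the sponsor and DSMB set Pt0 against the expected background of that event. Regenerate Table S2 without the overlapping rows, and state its stopping probability at the background rate and at the rates of concern.

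As an illustration of what step 3 can gain, a Pocock-type boundary with N = 44 and alpha near 5%, set against bleeding alone, would stop on a doubling with probability 51% (10 to 20%), 69% (15 to 30%) or 83% (20 to 40%). A composite event would have a different background and would need its own calculation.

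The cost is protocol and charter wording, one regenerated table, and some dependence on unblinded causality judgement for non-bleeding events. No new data are needed.

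### Section 10.5.2 compares a count of toxic events with a boundary built for patients; its 5% error holds per arm only if each patient counts once, and the event definition, one table row and the trial-level error also need correcting

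*Protocol*

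**What the plan says.** Section 10.5.2 sets the protocol's only numerical stopping boundary.

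- **Scope:** "We plan to monitor toxicity within each arm".
- **Unit counted:** "The cumulative number of grade 3 or 4 toxic events will be monitored after each person is enrolled". The sentences that follow keep to a cumulative number of toxic events.
- **Decision:** if the count after a given person "is greater than or equal to the associated boundary value bi then the combination treatment is rejected for safety considerations".
- **Boundary:** "Table S2. Toxicity Boundaries, N = 44, Pt0 = 0.33, and alpha=0.05". The first column is headed "Minimum Number of Subjects". One row runs from 35 to 37 subjects with boundary 20; the next runs from 36 to 40 with boundary 21.
- **Claimed property:** "there is only a 5% chance of stopping the trial early for lack of safety if the true toxicity rate is less than 33" per cent.
- **Alternative:** the same paragraph mentions a second, flexible approach at the time of DSMB reports. It is based on the proportion of subjects with SAEs and has no boundary.

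On severity, section 8.2 has the investigator record "Severity (mild, moderate, severe"). The protocol defines no numbered grades.

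**The concern.** A boundary derived for a rate among 44 patients assumes that each patient adds 0 or 1 to the count. A cumulative count of events can rise by more than one per patient. Patients with subarachnoid hemorrhage can plausibly have several serious complications each; section 8.3 lists more than 50 anticipated ones. Comparing events with a patient boundary then stops too easily, and the error rate given to the DSMB is not the one the rule has.

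Three further points make the rule hard to apply as written:

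- Grade 3 or 4, taken literally, leaves out a fatal event, and the grades cannot be read off the severity field that is collected.
- At 36 or 37 subjects a count of 20 means stop under one row and continue under the next.
- The 5% is worded as the chance of stopping the trial, but two arms are each monitored against the boundary.

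**Working it through.** **Inputs.** From section 10.5.2: the Table S2 boundaries b(n) for n = 4 to 44, reference rate 0.33, and stopping when the count is at or above b(n). Events per affected patient are not in the protocol and are varied below as an assumption.

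**Step 1: the plan's own figure, counting patients.** Let each patient have a toxicity with probability p, at most once. Let f(n, k) be the probability that k of the first n patients are affected and no boundary has been reached:

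f(n, k) = f(n−1, k)(1−p) + f(n−1, k−1)p.

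All mass with k ≥ b(n) is removed at each n and added to the stopping probability. For one arm:

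- p = 0.33: 5.31% with boundary 20 at n = 36–37, and 5.29% with boundary 21.
- p = 0.327: 5.01% and 4.98%.
- p = 0.30: 2.9%.
- p = 0.25: 1.0%.

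The stated 5% is reproduced to rounding. Table S2 is therefore a patient boundary.

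**Step 2: the overlap.** 5.31% − 5.29% = 0.02 percentage points. The ambiguity matters for the decision at those two looks, not for the overall error.

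**Step 3: counting events as written.** Use the same recursion, but let an affected patient contribute 1 + Poisson(m − 1) events, so that m is the mean number of events per affected patient. With boundary 20 at n = 36–37:

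| m (assumed) | 33% of patients affected | 25% of patients affected |
|---|---|---|
| 1 | 5.3% | 1.0% |
| 1.05 | 10.6% | 2.7% |
| 1.1 | 16.7% | 5.0% |
| 1.25 | 36.6% | 14.1% |
| 1.5 | 64.9% | 33.8% |
| 2 | 91.1% | 68.5% |

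At 33% affected, the error doubles when affected patients average 1.05 events and triples at 1.1.

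**Step 4: two arms.** With the arms independent and both at 33%, counting patients, the chance that at least one crosses is 1 − (1 − 0.0531)² = 0.1034 with boundary 20, or 1 − (1 − 0.0529)² = 0.103 with boundary 21: about 10.3%. With both at 25% it is 1 − (1 − 0.010)² = 0.020, or 2.0%.

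**Step 5: definition of a qualifying event.** The rule needs grades 3 and 4. Section 8.2 supplies three severity words and section 8.1 a definition of seriousness that includes death. Nothing maps either one to grades 3 and 4, and neither grade covers a fatal event on the wording used.

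**The case against.** **The patient-level reading is natural.** The text speaks of a toxicity rate, the table is indexed by subjects, and the alternative approach uses a proportion of subjects. This probably is what was meant, and under it the boundary performs as stated. But the sentences that define the count say events each time, and a stopping rule has to be applied as written.

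**A reader might infer that the table lacks its 5% error.** The documents do not support that. Per patient and per arm it is 5.3% at exactly 33% and at or below 5% up to about 32.7%, and the claim is made for rates below 33%. The 5% fails materially only if events are counted, or if it is read as the chance that either arm triggers. The 10.3% for either arm also needs both arms at 33%.

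**A reader might infer that a fatal bleed would pass unnoticed.** That does not follow either. Death is an SAE (section 8.1), so the SAE-based approach would include it. Mortality is a prespecified safety outcome (section 1.1). The adjudication committee forwards dangerous trends to the DSMB chair (section 8), the DSMB can halt the study at any time (section 8.2), and the medical safety monitor can go directly to the DSMB chair (section 12.4). The gap is in the counting rule, not in the whole safety system. The SAE approach has no boundary, so it does not repair Table S2.

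**A reader might infer that 33% is the wrong reference because section 8.5 puts background bleeding at 10–20%.** The two quantities differ: the 33% covers all grade 3 or 4 toxicity, the 10–20% covers major or clinically relevant non-major bleeding only. This comparison does not show an error in the rule.

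**The DSMB charter prevails over conflicting protocol text (section 8.6).** It may already settle these points, but it is not at hand, and its priority does not correct what section 10.5.2 states.

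**Conclusion.** The point holds in a limited form. Table S2 is sound to rounding as a per-arm, per-patient boundary. The rule as worded counts events, and then its error is not 5% unless almost no patient has more than one event. Its size cannot be fixed from the protocol: over the assumed range of 1.05 to 1.5 events per affected patient, with 33% of patients affected, it runs from 10.6% to 64.9%. Those figures also rest on the assumed Poisson form for repeat events and on patients being independent.

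The omission of fatal events and the undefined grading scale are defects of the literal wording. The row overlap is a clarity defect worth 0.02 percentage points. The trial-level error is a restatement: about 5.3% per arm and about 10.3% for either arm at 33%. All of this should be settled before the DSMB relies on the rule.

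**What to change.** - Replace the cumulative number of events with the number of patients who have had at least one qualifying event. If events really are meant, Table S2 has to be re-derived with a stated assumption on events per patient.
- Define a qualifying event on the severity scale that is collected, or add the grading scale to data collection, and state that fatal events count.
- Remove the overlap, for example by making the second row 38–40, after checking against the original derivation.
- State the error as about 5.3% per arm and about 10% for either arm at a 33% rate. If 5% for the trial is intended, re-derive the boundary.
- Carry the same wording into the DSMB charter.

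The cost is a wording amendment and one corrected table row; patient counting needs no new data or boundary. Whether to add a boundary specific to bleeding, and at what rate, is for the sponsor and the DSMB.
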